5.2.4 Electrocardiogram

5.2.4.1 12-lead resting ECG

Twelve-lead resting ECGs (I, II, III, aVR, aVL, aVF, V1 - V6) will be recorded using a computerised electrocardiograph (Cardionics SA, Brussels, Belgium) at the time points given in the [Flow Chart](#).

In order to achieve a stable heart rate at rest and to assure high quality recordings at comparable resting phases, all ECGs will be recorded for 10-sec duration after the subjects have rested for at least 5 min in a supine position. The site personnel will be instructed to assure a relaxed and quiet environment so that all subjects are at complete rest during the recordings. ECG assessment will always precede all other study procedures of the same time point (except blood drawing from an intravenous cannula which is already in place) to avoid impact of sampling on the ECG quality.

Electrode placement will be performed according to the method of Wilson, Goldberger and Einthoven. Precise electrode placement will be marked with an indelible mark on the skin to allow reproducible placement on day 1 and 2.

Triple ECGs (recorded within 180 sec) will be recorded at screening, as the baseline before drug administration and up to 30 hours after start of infusion. At all other time points single ECGs will be recorded.

All locally printed ECGs will be evaluated by the investigator or a designee.

ECGs may be repeated for quality reasons (like alternating current artefacts, muscle movements, electrode dislocation). For time points with triple ECGs, all three single ECGs will be repeated. For the repeats due to quality reasons, only the repeated ECG recordings will be used for analysis provided quality was better than with the initial ECG.

Additional (unscheduled) ECGs may be collected by the investigator for safety reasons. These ECGs are assigned to the prior scheduled time point. Unscheduled ECGs will not be included into the statistical analysis of interval lengths (if analysis is done).

For the inclusion or exclusion (see [Section 3.3](#)) of a subject and for the assessment of cardiac safety during the study, the QT and QTcB values generated by the ECG machines or their manual corrections by the investigators will be used. In doubtful cases, ECGs may be sent upfront for external evaluation. In this case, these externally measured results would overrule any other results obtained.

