7.2 NULL AND ALTERNATIVE HYPOTHESES

Safety and tolerability of the different dose groups of BI 655088 are to be determined on the basis of the investigated parameters in comparison to placebo. It is not planned to test any statistical hypotheses with regard to these variables in a confirmatory sense. Instead, they will be described in their entirety and evaluated by descriptive statistical methods.

Confidence intervals will be computed and will have to be interpreted in the perspective of the exploratory character of the study, i.e. confidence intervals are considered as interval estimates for effects.

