7.3.3 Safety analyses

Safety will be assessed for the endpoints listed in [Section 5.2.1](#). The TS as defined in [Section 7.3](#) will be included in the safety analyses.

Safety analyses will be descriptive in nature and will be based on BI standards.

Treatments will be compared in a descriptive way. The placebo control group in the safety evaluation will consist of all placebo treated subjects, regardless of the dose group in which they were treated. The active treatment groups will be compared to the placebo group in a descriptive way. Tabulations of frequencies/proportions will be used for the evaluation of categorical (qualitative) data, and tabulations of descriptive statistics will be used to analyse continuous (quantitative) data.

The analyses will be done by 'treatment at onset'.

Measurements (such as ECG, vital signs, or laboratory parameters) or AEs will be assigned to treatments (see [Section 4.1](#)) based on the actual treatment at the planned time of the measurement or on the recorded time of AE onset (concept of treatment emergent AEs). Therefore, measurements planned or AEs recorded prior to administration of trial medication will be assigned to 'screening', those between start of drug administration until the end of trial visit will be assigned to the treatment period, and those after the end of trial examination will

be assigned to ‘post-treatment’. These assignments including the corresponding time intervals will be defined in detail in the TSAP.

Adverse events will be coded using the Medical Dictionary for Regulatory Activities (MedDRA). Frequency, intensity and causal relationship of AEs will be tabulated by treatment, primary system organ class and preferred term. SAEs, AESIs (see [Section 5.2.2.1](#)) and other significant AEs (according to ICH E3) will be listed separately.

Laboratory data will be compared to their reference ranges. Values outside the reference range will be flagged. Additionally, differences from baseline will be evaluated. Results of the oGTT, i.e. further plasma glucose and serum insulin measurements will be evaluated in the same way as laboratory data but presented separately. In addition, graphical representations of individual time-courses of plasma glucose and insulin measurements and the (geometric) mean time profiles will be presented.

Area under the curve will be calculated for glucose and insulin according to the linear trapezoidal rule.

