Changes in AUCs for glucose and insulin (oGTT measurements) from baseline to post-treatment will be compared between BI 655088 and placebo.

Descriptive statistics of bleeding time at the time points given in the [Flow Chart](#) and for the difference from baseline will be provided.

Descriptive statistics of vital signs and for the difference from baseline will be presented per planned time. ECG data will not be listed but clinically relevant abnormal findings will be reported as adverse events.

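### The plan secures no by-dose summary of 12-lead ECG intervals; adding one is a cheap improvement on reporting ECG through adverse events alone

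*Protocol*

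**What the plan says.** Protocol Section 5.2.1 names one primary endpoint, the number of subjects with drug-related AEs, and then further criteria of interest. Among these, 12-lead ECG and continuous ECG monitoring have their own bullets. The AE bullet mentions findings from the physical examination and local tolerability, not ECG.

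The general analysis text is broad. Section 7.2 says of the safety parameters: "Instead, they will be described in their entirety and evaluated by descriptive statistical methods". Section 7.3.3 opens with "Safety will be assessed for the endpoints listed in" Section 5.2.1. It adds "The active treatment groups will be compared to the placebo group in a descriptive way" and, for measured quantities, "tabulations of descriptive statistics will be used to analyse continuous (quantitative) data". The synopsis promises descriptive statistics for every endpoint.

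The ECG-specific text is narrower. Section 7.3.3 says: "ECG data will not be listed but clinically relevant abnormal findings will be reported as adverse events". Section 5.2.4.1 treats interval analysis as conditional: "Unscheduled ECGs will not be included into the statistical analysis of interval lengths (if analysis is done").

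**The concern.** The general rules lead a reader to expect ECG intervals to be tabulated by dose level and pooled placebo. The ECG-specific sentences commit only to AE reporting. Two teams working from this protocol could both comply and yet report differently: one with interval summaries, one with AEs only.

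Under the AE-only reading, a finding reaches the report only if the investigator judges it clinically relevant (Section 5.2.4.1). That investigator knows the treatment (Section 4.1.5.2), and Section 3.2 itself concedes that single-blind conditions may bias the observer when AEs are assessed. A modest shift shared by most subjects at one dose could be irrelevant in each individual and informative for the group. AE reporting is not designed to show such a shift.

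**Working it through.** No figure in the protocol is in dispute, so the check is mainly a comparison of text.

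**Step 1. Does AE reporting replace a summary elsewhere?** It does not.
- Section 5.2.2.2 makes clinically relevant changes in vital signs and laboratory tests into AEs. Section 5.2.3.2 does the same for bleeding time.
- Section 7.3.3 nevertheless evaluates each of these with differences from baseline. For vital signs it says: "Descriptive statistics of vital signs and for the difference from baseline will be presented per planned time".
- The ECG sentence follows directly and contains no such commitment.

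**Step 2. Is there other ECG analysis text?**
- Section 7.3.3 names ECG when it assigns measurements to treatments. Section 5.2.4.1 has rules for repeat and unscheduled recordings.
- These are attribution and data-handling rules. Neither specifies a summary.

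**Step 3. Do the measurements exist?**
- For eligibility and cardiac safety, Section 5.2.4.1 states that "the QT and QTcB values generated by the ECG machines or their manual corrections by the investigators will be used".
- The same section plans triple ECGs at screening, at baseline and up to 30 hours after the start of infusion, and electronic storage of all ECGs.
- Section 3.3.4.2 uses a numeric QTc change from baseline to stop escalation.
- Interval values are therefore produced and used during the trial. What is not secured is their place in the report.

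**Step 4. Does the same apply to continuous ECG?** Section 5.2.4.2 describes two-lead monitoring of rhythm and heart rate until 4 hours after the start of infusion. It names no interval measurement, so the lack of an interval table there is not a defect.

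**Step 5. What precision would a summary have?** The protocol gives no SD for ECG intervals. I assume 10 to 15 ms for change from baseline, at one time point, for one dose level against pooled placebo, with a common variance.
- Active n = 6. Pooled placebo n = 6 groups × 2 = 12 (Section 3.1). Degrees of freedom = 6 + 12 − 2 = 16, so t(0.975) = 2.120.
- SE = SD × √(1/6 + 1/12) = SD × 0.5, which is 5.0 ms at SD 10 and 7.5 ms at SD 15.
- 95% half-width = 2.120 × 5.0 = 10.6 ms, and 2.120 × 7.5 = 15.9 ms.

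This only indicates how finely a table could describe a shift. The AE route has no numeric threshold, so there is no matching figure to set against it.

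**The case against.** A reader might infer that the protocol contradicts itself outright, or that it bans ECG summaries. The documents do not support either reading. Withholding a listing is not the same as withholding a summary. The ECG-specific passages agree with one another: interval analysis is optional, central evaluation is optional (Sections 3.1.1 and 5.2.4.1), and relevant findings become AEs. A specific sentence that follows a general rule is ordinarily read as qualifying it. Section 7.2 is chiefly explaining why no confirmatory tests are done, and the synopsis row on safety criteria can be read as covering ECG through AEs. AEs tabulated by treatment are also a descriptive comparison with placebo. All of this stands, and it makes the point one of improvement.

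A reader might also infer that subjects are less well protected. That is not supported either. Results from the 12-lead and continuous ECG belong to the minimum data set for each safety review (Section 3.1), a numeric QTc rule governs escalation (Section 3.3.4.2), and recordings can be re-evaluated. Only the content of the report is affected.

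Finally, it can be said that this belongs in the statistical analysis plan, which is not shown and may settle it. That holds for layout and derivation details. Whether intervals are summarised at all, though, is something the protocol itself addresses, and it answers with an option. The synopsis argument is also limited: the same phrase covers laboratory tests, vital signs, oGTT and bleeding time, all of which Section 7.3.3 summarises.

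**Conclusion.** The point holds as a recommended improvement of minor to moderate weight. The protocol makes 12-lead ECG a criterion of its own and promises descriptive evaluation in general terms, but the only ECG-specific commitment runs through a relevance judgement made with knowledge of treatment. A group-level change in QTc, PR interval or QRS could go unreported although the recordings exist.

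This conclusion rests on the text and needs no assumed SD. The half-width of about 11 to 16 ms does depend on the assumed 10 to 15 ms. It should not be read as a power statement, because the trial is descriptive (Section 7.2) and its size is not based on power (Section 7.6).

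**What to change.** In Section 7.3.3, replace the ECG sentence with a commitment along these lines: *QT, QTc (correction named), PR interval and QRS from scheduled 12-lead ECGs, with triplicates averaged per time point, and their changes from baseline will be summarised descriptively by dose level and pooled placebo at each planned time. In addition, abnormal ECG findings judged clinically relevant will be reported as AEs.*

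In Section 5.2.4.1, delete the parenthesis that makes interval analysis conditional. Writing PR interval in full avoids confusion, since the protocol abbreviates pulse rate as PR. For continuous ECG, state that it is rhythm monitoring and is evaluated through clinically relevant findings reported as AEs.

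The cost is a data transfer and some programming, because the protocol does not say that interval values are entered in the CRF. No new recordings or readers are needed. The QTc rule in Section 3.3.4.2 is unchanged.

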7.3.4 Preliminary PK and PD analyses

A preliminary analysis of PK parameters (AUC_{0-168} and C_{max} of BI 655088), provided as individual values and geometric means, will be performed for

- dose levels 1, 2, 3, 4 (n) before proceeding to dose level 3, 4, 5, 6 (n+2)

In addition, exploratory analyses of pharmacodynamics will be performed for each dose level in parallel.

In contrast to the final PK/PD calculations, the preliminary analyses will be based on planned sampling times rather than on actual times, regardless of whether actual times were within the time windows or not. Therefore, minor deviations of preliminary and final results may occur. The preliminary analyses will provide individual and mean concentration/effect-time profiles and summary statistics of individual values without subject identification.

The preliminary PK/PD results will be distributed to the Investigator and the trial team.

Depending on the results of available preliminary PK/PD analyses, the tolerability and safety of the compound, and changes of dosing schedule (e.g. additional intermediate doses) additional PK/PD preliminary analysis may be performed based on the request of the Trial Clinical Monitor, the investigator, or Trial Clinical Pharmacokineticist. No formal preliminary PK/PD report will be written.

7.3.5 Pharmacokinetic analyses

The pharmacokinetic parameters listed in [Section 5.5.1](#) for BI 655088 will be calculated according to the BI SOP 'Standards and processes for analyses performed within Clinical Pharmacokinetics/Pharmacodynamics' ([001-MCS-36-472](#)).

Subjects who are not included in the PKS (refer to [Section 7.3.2](#)) will be reported with their individual plasma concentrations and individual pharmacokinetic parameters; however, they will not be included in descriptive statistics for plasma concentrations, pharmacokinetic parameters or other statistical assessment.

Only concentration values within the validated concentration range and actual sampling times will be used for the calculation of pharmacokinetic parameters. Concentrations used in the pharmacokinetic calculations will be in the same format provided in the bioanalytical report, (that is, to the same number of decimal places provided in the bioanalytical report).

7.4 HANDLING OF MISSING DATA

7.4.1 Safety

With respect to safety evaluations, it is not planned to impute missing values.

7.4.2 Plasma drug concentration - time profiles

Handling of missing PK data will be performed according to the relevant SOP of the Sponsor ([001-MCS-36-472](#)).

Drug concentration data identified with NOS (no sample available), NOR (no valid result), NOA (not analyzed), BLQ (below the lower limit of quantification), or NOP (no peak detectable) will be displayed as such and not replaced by zero at any time point (this rule also applies also to the lag phase, including the predose values).

7.4.3 Pharmacokinetic parameters

Handling of missing PK data will be performed according to the relevant SOP of the Sponsor ([001-MCS-36-472](#)).

For the non-compartmental analysis, concentration data identified with NOS, NOR or NOA will generally not be considered. Concentration values in the lag phase identified as BLQ or

NOP will be set to zero. All other BLQ/NOP values of the profile will be ignored. The lag phase is defined as the period between time zero and the first time point with a concentration above the quantification limit.

7.5 RANDOMISATION

Subjects will be randomised within each dose group in a 3:1 ratio, which reflects the ratio of subjects receiving active drug to placebo. Due to the fixed drug administration of the 4 first subjects within each dose group (1st subject active, 2nd subject placebo, 3rd and 4th subject active), the trial is called “partially-randomised”. Each dose group consists of 3 cohorts. The random numbers are assigned to the cohorts sequentially per dose group.

The sponsor will arrange for the randomisation as well as packaging and labelling of trial medication. The randomisation list will be generated using a validated system, which involves a pseudo-random number generator and a supplied seed number so that the resulting allocation is both reproducible and non-predictable.

The randomisation list will contain additional blocks to allow for subject replacement (refer to [Section 3.3.5](#)).

7.6 DETERMINATION OF SAMPLE SIZE

It is planned to include a total of 48 subjects in this trial. The planned sample size is not based on a power calculation. The size of 8 subjects per dose group (6 on active treatment, and 2 on placebo) is commonly used in single-rising dose studies of the present type and is in general considered as sufficient for the exploratory evaluation of single dose safety and pharmacokinetics ([R95-0013](#)).

Additional subjects may be entered to allow testing of additional intermediate doses within the planned dose range on the basis of experience gained during trial conduct (e.g. preliminary PK data), i.e. the actual number of subjects entered may exceed 48.

8. INFORMED CONSENT, DATA PROTECTION, TRIAL RECORDS

The trial will be carried out in compliance with the protocol, the principles laid down in the Declaration of Helsinki, in accordance with the ICH Harmonised Tripartite Guideline for Good Clinical Practice (GCP) and relevant BI.

The investigator should inform the sponsor immediately of any urgent safety measures taken to protect the study subjects against any immediate hazard, and also of any serious breaches of the protocol or of ICH GCP.

The rights of the investigator and of the sponsor with regard to publication of the results of this trial are described in a separate agreement between the investigator or the trial site and the sponsor. As a general rule, no trial results should be published prior to finalisation of the CTR.

Insurance Coverage: The certificate of insurance cover is made available to the investigator and each subject, and is stored in the ISF.

8.1 STUDY APPROVAL, SUBJECT INFORMATION, AND INFORMED CONSENT

This trial will be initiated only after all required legal documentation has been reviewed and approved by the respective Institutional Review Board (IRB) / Independent Ethics Committee (IEC) and competent authority (CA) according to national and international regulations. The same applies for the implementation of changes introduced by amendments.

Prior to a subject's participation in the trial, written informed consent must be obtained from each subject (or the subject's legally accepted representative) according to ICH GCP and to the regulatory and legal requirements of the participating country. Each signature must be personally dated by each signatory and the informed consent and any additional subject information form are to be retained by the investigator as part of the trial records. A copy of the signed and dated written informed consent and any additional subject information must be given to each subject or the subject's legally accepted representative.

The subject must be informed that his personal trial-related data will be used by Boehringer Ingelheim in accordance with the local data protection law. The level of disclosure must also be explained to the subject.

The subject must be informed that his medical records may be examined by authorised monitors (Clinical Monitor Local/Clinical Research Associate) or Clinical Quality Assurance auditors appointed by Boehringer Ingelheim, by appropriate IRB/IEC members, and by inspectors from regulatory authorities.

8.2 DATA QUALITY ASSURANCE

A quality assurance audit/inspection of this trial may be conducted by the sponsor or sponsor's designees, by IRBs/IECs, or by regulatory authorities. The quality assurance

auditor will have access to all medical records, the investigator's trial-related files and correspondence, and the informed consent documentation of this clinical trial.

The data management procedures to ensure the quality of the data are described in detail in the trial data management and analysis plan (TDMAP) available in the TMF.

8.3 RECORDS

CRFs for individual subjects will be provided by the sponsor. For drug accountability, refer to [Section 4.1.8](#).

8.3.1 Source documents

Source documents provide evidence for the existence of the subject and substantiate the integrity of the data collected. Source documents are filed at the investigator's site.

All data reported in the CRFs must be consistent with the source data or the discrepancies must be explained.

The investigator may need to request previous medical records or transfer records, depending on the trial.

8.3.2 Direct access to source data and documents

The investigator/institution will permit trial-related monitoring, audits, IRB/IEC review and regulatory inspection, providing direct access to all related source data/documents. CRFs and all source documents, including progress notes (if applicable) and copies of laboratory and medical test results must be available at all times for review by the sponsor's clinical trial monitor, auditor and inspection by health authorities (e.g. FDA). The Clinical Research Associate/on site monitor and auditor may review all CRFs, and written informed consents. The accuracy of the data will be verified by reviewing the documents described in [Section 8.3.1](#).

8.4 LISTEDNESS AND EXPEDITED REPORTING OF ADVERSE EVENTS

8.4.1 Listedness

To fulfil the regulatory requirements for expedited safety reporting, the sponsor evaluates whether a particular AE is 'listed', i.e. is a known side effect of the drug. Therefore a unique reference document for the evaluation of listedness needs to be provided. For BI 655088 this is the current version of the Investigator's Brochure ([c02156503-03](#)). The current version of this reference document is to be provided in the ISF. No AEs are classified as listed for matching placebo, study design, or invasive procedures.

8.4.2 Expedited reporting to health authorities and IECs/IRBs

Expedited reporting of serious adverse events, e.g. suspected unexpected serious adverse reactions (SUSARs) to health authorities and IECs/IRBs, will be done according to local regulatory requirements. Further details regarding this reporting procedure are provided in the Investigator Site File.

